4.3.3 Subject completion

Subjects will be considered complete for the purpose of this study once they have completed all procedures. The end of the study is defined as the last assessment of the last subject undergoing the study.

4.3.4 Discontinuation criteria

It is possible that the Sponsor, REC or HRA request termination of the study if there are concerns about conduct or safety, or due to a change in the opinion of the Ethics Committee.

When the Sponsor is aware of information on matters concerning the quality, efficacy, and safety of the study drug, as well as other important information that may affect proper conduct of the clinical study, the Sponsor may discontinue the clinical study and send a written notice of the discontinuation along with the reasons to the Investigators. Patients will be informed that they have the right to withdraw from the study at any time for any reason, without prejudice to their medical care. The site Investigator/Chief Investigator can discontinue subjects from the study for any of the following reasons:

1. Occurrence of an unacceptable Adverse Event due to Grade 2 or above defined by the NCI Common Terminology Criteria for Adverse Events (version 5.0, 2017), adapted for this study -see [Appendix 2](#).
2. Subject request
3. Subject is lost to follow-up
4. Administrative reasons
5. Development of an intercurrent illness, condition, or procedural complication, which would interfere with the subject's continued participation
6. Patient becomes pregnant

The site Investigator/Chief Investigator also reserves the right to discontinue subjects in the interest of subject safety and welfare. Investigators must contact all participants and the hospital pharmacy (where applicable) to notify them of the termination of the study. In cases of an early termination (discontinuation), a follow-up telephone assessment will be performed 4 weeks \pm 3 days -see [Appendix 1](#).

4.3.5 Subject identification and replacement policy

After informed consent is obtained, patients who are screened will be assigned a 7-digit permanent identification number (subject ID) such that all patients given consecutive identification numbers in successive order of inclusion. The first 4 digits of the will be the designated research site ID, and the last 3 digits will be assigned at the research study centre (e.g., if the site ID is 4410, the third patient screened at 4410 site, would be given the number 4410003).

A patient who is screened but fails to proceed into baseline assessment (e.g., because entry criteria were not met or enrolment did not occur within the specified time frame) may be considered for screening again. Re-screening will be permitted by the site Investigator on a case-by-case basis. A new informed consent form will be signed in any case of re-screening. A new subject ID will be assigned to the subject. Patients who are discontinued will be replaced. Each replacement is by a default a new subject, who will be assigned a completely new subject ID.

5. PHARMACOLOGICAL CHALLENGE AGENT

Patients who are eligible to participate in the study will receive XBD173.

5.1 XBD173

5.1.1 Preparation

XBD173 will be formulated by Royal Free Hospital for administration in capsules. XBD173 will be formulated in accordance with regulatory requirements of the Royal Free Hospital pharmacy.

5.1.2. Administration

Oral

5.2 Labelling

The study drug will be labelled by Royal Free Hospital for administration in capsules in accordance with local regulatory requirements.

5.3 Study drug accountability

Accountability for the study drug at the study site is the responsibility of the site Investigator. He/she will ensure that the study drug is used only in accordance with this protocol. Where allowed, the site Investigator may choose to assign some of the drug accountability responsibilities to a pharmacist or other appropriate individual.

Drug accountability records indicating the drug's delivery date to the site, inventory at the site, use by each subject, and end-of-study destruction and disposal of the drug, will be maintained by each clinical site. These records will adequately document that the subjects were provided the doses as specified in the protocol. Site's accountability pharmacy logs can be used to confirm if sites can destroy/dispose of unused drug in line with their local requirements.

5.4 Treatment assignment

All patients will receive XBD173 at 90mg once daily. Patient 3 onwards will escalating to 90mg twice daily after 2 weeks.

5.5 Concomitant medications

5.5.1 Permitted concomitant medications

Approved endothelin receptor antagonists, phosphodiesterase-5 type inhibitors and/or prostacyclin analogues are permitted for the treatment of PAH. The dose must be stable for at least 1 month prior to entry into the study.

5.5.2 Patients taking one of the following medications will be excluded:

- P450 CY3A4 inhibitors
 - Potent: Boceprevir, Clarithromycin, Cobicistat, Idelalisib, Itraconazole, Ketoconazole, Nelfinavir, Ritonavir, Saquinavir, Telaprevir, Telithromycin, Voriconazoleb
 - Moderate: Aprepitant, Conivaptan, Crizotinib, Diltiazem, Dronedarone, Erythromycin, Fluconazole, Imatinib, Isavuconazole, Nefazodone, Netupitant, Nilotinib, Posaconazolee, Tofisopam, Verapamil
 - Unclassified: Delavirdine
- P450 CY3A4 inducers
 - Potent: Carbamazepine, Enzalutamide, Fosphenytoin, Mitotane, Phenytoin, Rifampicin
 - Moderate: Bosentan, Efavirenz, St John's wort
 - Unclassified: Barbiturates, Nevirapine, Primidone, Rifabutin, Rifapentine
- oral contraceptives

- oral anticoagulants or antiplatelet agents other than low dose aspirin
- levothyroxine

6. VISIT AND ASSESSMENT SCHEDULE

For a tabulated summary of all visits and assessments see the Schedule of Events, [Appendix 1](#). Screening and baseline assessments can be performed on a single day as long as this is feasible and the patient agrees to a long study visit. On those occasions, procedures which are common among screening and baseline should be performed once, unless deemed clinically necessary to repeat.

6.1 Screening assessment (before Week 0)

The screening assessment should be performed no more than 28 days prior to the baseline visit. Participants' eligibility will be determined using data collected during their routine hospital appointment:

- Review of inclusion/exclusion criteria
- Obtain written informed consent
- Demographics
- Medical and medication history (incl. smoking and alcohol history)
- Physical examination
- Concomitant medications
- Vital signs: (i) Resting supine blood pressure (BP), (ii) pulse measurement, (iii) temperature, (iv) pulse oximetry (incl. respiratory rate), (v) height, and (vi) weight
- World Health Organisation (WHO) Functional Class
- Six-minute walk test (6MWT) and Borg dyspnoea index
- Electrocardiogram (ECG)
- Blood samples for haematology, clinical chemistry, TSPO rs6971 genotype and serum pregnancy test whereas indicated (for women of childbearing potential)

6.2 Baseline assessment (Week 0)

The patient will undergo the following procedures:

- Review of test results and reports with the Study Physician
- Urinary pregnancy test where indicated
- Concomitant medications
- Record of readings from implanted devices
- Research blood sampling

Following completion of the above procedures, each patient will receive their first dose of XBD173.

6.3 Telephone assessment (Week 1 ± 3 days)

Patients will receive a telephone call at the end of Week 1 to check concomitant medications, and for the occurrence of AEs.

6.4 Hospital assessment (Week 2 ± 3 days)

Patients will attend for safety, urinary pregnancy test (if indicated) and research blood tests, to check concomitant medications, and for the occurrence of AEs. Following completion of these procedures and review of the blood tests, the physician can increase the dose of XBD173 to 90mg twice daily.

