	
Site Physician
 
10. Patients with a history of uncontrolled systemic hypertension
 
11. Acute infection (including eye, dental, and skin infections)
 
12. Chronic inflammatory disease including HIV, and Hepatitis B
 
13. Women of childbearing potential who are pregnant or breastfeeding (if applicable)
 
14. Patients who have received an Investigational Medicinal Product (IMP) within 5 half-lives of the last dose of the IMP or 1 month (which ever is greater) before the baseline visit
 
15. Use of the following medications or therapies:
 
 • Severe and moderate P450 CY3A4 inhibitors: Boceprevir, Clarithromycin, Cobicistat, Idelalisib, Itraconazole, Ketoconazole, Nelfinavir, Ritonavir, Saquinavir, Telaprevir, Telithromycin, Voriconazoleb, Aprepitant, Conivaptan, Crizotinib, Diltiazem, Dronedarone, Erythromycin, Fluconazole, Imatinib, Isavuconazole, Nefazodone, Netupitant, Nilotinib, Posaconazolee, Tofisopam, Verapamil, Delavirdine. • Severe and moderate P450 CY3A4 inducers: Carbamazepine, Enzalutamide, Fosphenytoin, Mitotane, Phenytoin, Rifampicin, Bosentan, Efavirenz, St John's wort, Barbiturates, Nevirapine, Primidone, Rifabutin, Rifapentine. • Oral contraceptives • Oral anticoagulants or antiplatelet agents other than low dose aspirin • Levothyroxine

PHARMACOLOGICAL CHALLENGE:
	
For the first 2 participants, XBD173 will be given orally 90mg once daily for 8 weeks, in addition to their usually medication.
 
For the next 4 participants, XBD173 will be given orally 90mg once daily for the first 2 weeks, in addition to their usually medication, and then orally 90mg twice daily for 6 weeks.
 
Enrolment will be staggered so that each participant will start dosing at least 2 weeks after the previous participant.
 
Patients will be monitored for safety by clinic visit at the end of Weeks 2, 4, and 8. They will be followed for a further 4 weeks off study treatment.
 
Blood levels of XBD173 will be measured in each patient at the end of Week 8.

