4.1 Overall study design and plan

Patients will be invited to participate by their local pulmonary hypertension hospital. The first 2 participants will be treated with XBD173 90mg once daily for 8 weeks. The first patient will be followed for at least 2 weeks before the second patient starts the XBD173. Subsequent participants will be treated with XBD173 90mg once daily for 2 weeks at intervals of at least 2 week and if the drug is tolerated (defined as an absence of grade 2 adverse events) the dose will be increased to 90mg twice daily for a further 6 weeks. The total period of treatment for each patient is 8 weeks, followed by 4 weeks follow up off XBD173. If a grade 2 AE occurs during 90mg once daily dosing, the participant will be withdrawn. If a patient does not tolerate 90mg twice daily, the local PI will determine whether to stop XBD173, reduce the dose to 90mg once daily or pause dosing and restart at 90mg once daily.

The starting dose of 90mg OD is based on experience from studies of XBD173 in healthy volunteers and in patients with multiple sclerosis.

Rupprecht et al randomised 71 healthy volunteers to 7 days treatment with placebo, 10, 30, or 90 mg/day XBD173 or 2 mg/day alprazolam (PMID: 19541954). The number of side effects reported with XBD173 was comparable to the incidence in the placebo group. In contrast, a much higher incidence was reported by the alprazolam-treated group.

In addition, 4 studies have been sponsored by Imperial College London using XBD173. In all studies XBD173 was well tolerated with no SAEs:

17/LO/0566. This study recruited healthy volunteers (n=31) and people with MS (n=12) and administered XBD173 90mg for 7 days. (To be submitted for publication September 2022).

14/LO/0343. This study recruited people with MS (n=6) and administered a single dose of XBD173 (90mg) prior to PET scanning with 11C-GE180. (PMID: 30796709).

12/LO/0735. This study recruited healthy volunteers (n=6) and administered a single dose of XBD173 ranging from 10mg-90mg prior to PET scanning with 11C-PBR28. (PMID: 24623083).

13/LO/1916. This study recruited healthy volunteers (n=6) and people with MS (n=6) and administered a single doses of XBD173 (90mg) prior to PET scanning with 11C-PBR28. (PMID: 30796709)

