Assessment Name	Assessment 1 (screening)	Assessment 2 (baseline)	Telephone assessment	Assessment 3	Telephone assessment	Assessment 4	Assessment 5	Assessment 6	Unscheduled visit
Location	Clinic	Clinic/Home	📞	Clinic	📞	Clinic	Clinic	Clinic/Home	Unscheduled assessment
Time (weeks)	Before Week 0	Week 0	Week 1	Week 2	Week 3	Week 4	Week 8	Week 12	Clinic/Home
Assessment Window (days)	0	Within 7 days baseline	± 3 days	± 3 days	± 3 days	± 3 days	± 3 days	± 3 days	when needed
Inclusion/Exclusion criteria	X	-	-	-	-	-	-	-	n/a
Written informed consent	X	-	-	-	-	-	-	-	-
Demographics	X	-	-	-	-	-	-	-	-
Medical and medication history	X	-	-	-	-	-	-	-	X
Physical examination	X	-	-	-	-	X	X	-	X
Concomitant medications	X	X	X	X	X	X	X	X	X
Vital signs	X	-	-	-	-	X	X	-	X
WHO Functional Class	X	-	-	-	-	-	-	-	-
Six-minute walk test (6MWT)	X	-	-	-	-	-	-	-	-
Borg Dyspnoea Index	X	-	-	-	-	-	-	-	-
Haematology blood tests	X	-	-	X	-	X	X	-	X ^b
Clinical chemistry tests	X	-	-	X	-	X	X	-	X ^b
TSPO genotype test	X								
Serum pregnancy test	X ^a	-	-	-	-	-	-	-	-
Urinary pregnancy test		X ^a		X ^a		X ^a	X ^a		X ^a
Home body weight and ankle swelling self-check	-	-	X	-	X	-	-	-	-
XBD173 assay	-	-	-	-	-	X	X	-	-
Research blood samples	-	X	-	X	-	X	X	X	-
Electrocardiogram (ECG)	X	-	-	-	-	X	X	-	-
Administration of XBD173	-	X	-	-	-	-	-	-	X ^b
Review of the diary, XBD173 collection and reconciliation	-	-	-	-	-	X	X	X	-
Report of Adverse Events , if any	-	X	X	X	X	X	X	X	-

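### From participant 3 onwards the dose is doubled at Week 2 with no scheduled check that the lead-in doses were taken; the protocol's own diary review and capsule reconciliation first occur at Week 4

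*Protocol*

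**What the plan says.** All references are to the protocol.

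- **Who escalates.** Section 5.4: "Patient 3 onwards will escalating to 90mg twice daily after 2 weeks". The Study Summary gives the lead-in: "For the next 4 participants, XBD173 will be given orally 90mg once daily for the first 2 weeks". Participants 1 and 2 stay on 90 mg once daily for all 8 weeks.
- **The test for escalation.** Section 4.1: "if the drug is tolerated (defined as an absence of grade 2 adverse events) the dose will be increased to 90mg twice daily".
- **The Week 2 visit.** Section 6.4 covers safety and research bloods, a pregnancy test if indicated, concomitant medication and adverse events. It then says: "Following completion of these procedures and review of the blood tests, the physician can increase the dose of XBD173 to 90mg twice daily".
- **When intake is checked.** The Appendix 1 row "Review of the diary, XBD173 collection and reconciliation" is marked at Weeks 4, 8 and 12 and at no earlier time. The XBD173 assay is marked at Weeks 4 and 8. Sections 6.6 and 6.7 place reconciliation and the assay at the Week 4 and Week 8 visits.
- **General accountability.** Section 5.3 makes the site investigator responsible for use according to protocol and asks for records of each subject's use. It sets no time point for reviewing them.

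**The concern.** The once-daily lead-in is there to show that a given participant tolerates 90 mg a day before the dose doubles. A clean adverse-event record shows this only if the capsules were swallowed. Someone who took few or none would very likely also have no drug-related grade 2 event, and would meet the definition of tolerated in 4.1.

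The protocol already has the right tools, a diary and a capsule reconciliation. It schedules them after the decision they would inform. The step is to 180 mg/day, and the most that 4.1 cites in humans is 90 mg a day for 7 days ("7 days treatment with placebo, 10, 30, or 90 mg/day XBD173" in one study; the sponsor's own studies used 90 mg for 7 days or single doses of up to 90 mg). So the participant's own lead-in is the most direct evidence available for that individual at the time of the increase.

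**Working it through.** The protocol states no figure to reproduce. The check is a reading of each contact up to the decision, followed by day counts from the visit windows.

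**1. Scheduled contacts up to and including escalation**

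| Contact | Content | Intake check? |
|---|---|---|
| Week 0 (6.2) | Test results, pregnancy test if indicated, concomitant medication, device readings, research blood, first dose | No |
| Week 1 call (6.3, Appendix 1) | Concomitant medication, adverse events; weight and ankle-swelling self-check | No |
| Week 2 visit (6.4, Appendix 1) | Safety and research bloods, pregnancy test if indicated, concomitant medication, adverse events | No |
| Week 4 visit (6.6, Appendix 1) | Includes diary review, collection, reconciliation and XBD173 assay | Yes, the first |

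Scheduled intake checks before or at escalation: 0. The Study Summary mentions drug levels only at Week 8, which would put the first assay later still and does not alter this count.

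**2. Timing.** Inputs: Week 2 ± 3 days (6.4) is days 11 to 17; Week 4 ± 3 days (6.6) is days 25 to 31. Assumption: the dose is raised on the day of the Week 2 visit.

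- Lead-in doses unchecked at escalation, at one a day: nominally 14, range 11 to 17.
- Days from escalation to the first check: nominally 28 − 14 = 14; shortest 25 − 17 = 8; longest 31 − 11 = 20.
- Scheduled 90 mg doses in that interval, at two a day: nominally 2 × 14 = 28; range 2 × 8 = 16 to 2 × 20 = 40. This is an upper bound on doses taken, because someone who missed once-daily doses may also miss twice-daily ones.

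**3. Dose.** 2 × 90 = 180 mg/day; 180 / 90 = 2 times the highest daily dose cited in 4.1.

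**4. What the earlier participants contribute.** The Study Summary says: "Enrolment will be staggered so that each participant will start dosing at least 2 weeks after the previous participant". Count days from participant 1's start.

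- Participant 3 starts no earlier than day 14 + 14 = 28 and escalates no earlier than day 28 + 11 = 39.
- Participant 1's Week 4 check falls on days 25 to 31, at least 39 − 31 = 8 days before any escalation, if that participant is still on study.
- Participant 2, starting on day 14 at the earliest, has that check on days 14 + 25 = 39 to 14 + 31 = 45. With minimum stagger this coincides with participant 3's Week 2 window, days 28 + 11 = 39 to 28 + 17 = 45.

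So at least one intake-checked participant at 90 mg once daily is expected before the first escalation. That says nothing about whether participant 3 took the lead-in.

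**The case against.** The strongest reply is that the sections agree on the sequence, and that one more compliance check is a matter of preference that may sit in a dispensing procedure or case report form not shown here. Section 5.3 already requires use according to protocol and records of use. The wording of 6.4 is permissive, so a physician seeing the participant face to face can ask about missed doses. After escalation there is a Week 3 call, a Week 4 visit with ECG, bloods and assay, and remote review twice a week. If twice-daily dosing is not tolerated, "the local PI will determine whether to stop XBD173, reduce the dose to 90mg once daily or pause dosing".

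Much of this stands, and it is why the point is small. It does not remove the point. Section 5.3 ties no review to the Week 2 decision, 4.1 says the dose will go up when there is no grade 2 event, and the later monitoring detects trouble after the step. The protocol itself fixes the check after the decision.

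Three stronger readings might be inferred, and the documents support none of them.

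- *The gap exposes participants to an untested dose.* A fully adherent participant also goes to 180 mg/day. The gap adds only that someone may get there with fewer prior 90 mg doses, and nothing in the protocol shows that this is harmful. Section 4.1 reports good tolerability and no serious adverse events in the sponsor's four studies.
- *Adherence is not monitored.* It is, from Week 4. Diary review and reconciliation at that visit can still document lead-in intake in retrospect.
- *Poor intake should count as not tolerated.* Under 4.1 a grade 2 event on once-daily dosing means withdrawal. Folding adherence into that definition would confuse two different things.

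**Conclusion.** The concern holds as a minor matter of scheduling. For participants 3 onwards, the Week 2 doubling rests on the absence of grade 2 adverse events, completed procedures and blood-test review. The first scheduled check of capsule intake comes nominally 14 days (8 to 20) later.

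It applies to the 4 participants planned for escalation out of up to 6, plus any replacement who escalates. It has consequences only for one who skipped lead-in doses. The protocol gives no adherence rate, so the chance of that cannot be estimated. The day counts assume escalation on the day of the Week 2 visit. The change is worth considering because it is nearly free and comes before a dose above any the protocol cites in humans. It is not a serious safety defect, and no effect on the primary measures is claimed.

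**What to change.** 1. **Appendix 1:** mark the diary review, collection and reconciliation row at Week 2, in addition to Weeks 4, 8 and 12.
2. **Section 6.4:** add a third condition to the escalation sentence, alongside the procedures and blood-test review: diary review and capsule count confirming that lead-in doses were taken.
3. **Section 4.1:** leave the definition of tolerated as it is, but make the increase subject to the 6.4 check.
4. **Section 4.1:** state that a participant not escalated because of poor lead-in intake may continue on 90 mg once daily, the regimen of participants 1 and 2. Say that the rule withdrawing anyone unable to continue the prescribed dose to 8 weeks does not apply to this case. Without this, holding the dose would create a route that 5.4 and the withdrawal rule do not cover.

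**Cost.** A few minutes of staff time at a clinic visit that already takes place, and participants must bring their diary and remaining capsules. No extra visit or blood is needed. A participant with poor lead-in intake may have less exposure, or none, at 180 mg/day within the fixed 8 weeks, in a group of only 4.

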6.5 Telephone assessment (Week 3 ± 3 days)

Patients will receive a telephone call at the end of Week 3 to check concomitant medications, and for the occurrence of AEs

6.6 Assessment on Week 4 (Week 4 ± 3 days)

The patient will be invited to attend their local hospital or a home assessment will be made at the end of Week 4 in order to undergo the following procedures:

- Physical examination
- Concomitant medications
- Document AEs
- Vital signs: (i) Resting supine BP, (ii) pulse measurement, (iii) temperature, (iv) pulse oximetry (incl. respiratory rate), and (v) weight
- ECG
- Blood samples for haematology and clinical chemistry, and urinary pregnancy test (if indicated)
- Blood sample for XBD173 levels
- Research blood sampling
- XBD173 collection and reconciliation

6.7 Assessment on Week 8 (Week 8 ± 3 days)

The patient will be invited to attend their local hospital or a home assessment will be made at the end of Week 8 in order to undergo the following procedures:

- Physical examination
- Concomitant medications
- Document AEs
- Vital signs: (i) Resting supine BP, (ii) pulse measurement, (iii) temperature, (iv) pulse oximetry (incl. respiratory rate), and (v) weight
- ECG
- Blood samples for haematology and clinical chemistry, and urinary pregnancy test (if indicated)
- Blood sample for XBD173 levels
- Research blood sampling
- XBD173 collection and reconciliation

6.8 Assessment on Week 12 (Week 12 ± 3 days)

The patient will be invited to attend their local hospital or a home assessment will be made at the end of Week 12 in order to undergo the following procedures:

- Physical examination
- Concomitant medications
- Document AEs
- Vital signs: (i) Resting supine BP, (ii) pulse measurement, (iii) temperature, (iv) pulse oximetry (incl. respiratory rate), and (v) weight
- ECG
- Research blood sampling

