4.3.1 Inclusion criteria

1. Subjects aged between 18-75 years old
2. PAH which is: idiopathic; PAH heritable; PAH associated with connective tissue disease; PAH after \geq 1 year repair of congenital systemic to pulmonary shunt; or PAH associated with anorexigens or other drugs.
3. Resting mean pulmonary artery pressure \geq 25 mmHg, pulmonary capillary wedge pressure \leq 15 mmHg, PVR $>$ 5 wood units, and normal or reduced cardiac output, as measured by a previous right heart catheterisation (RHC).
4. Have an insertable FDA/CE cardiac rhythm monitor and pulmonary artery pressure monitor that captures cardiopulmonary haemodynamics and daily activity.
5. Six-minute walking distance $>$ 50m at entry
6. Stable on an unchanged PAH therapeutic regime comprising at least 2 therapies licensed for PAH (any combination of endothelin receptor antagonist, phosphodiesterase inhibitor or prostacyclin analogue) for at least 1 month prior to screening
7. Subjects willing to be genotyped for genes that influence XBD173 activity
8. Able to provide written informed consent prior to any study mandated procedures
9. Contraception: Women of childbearing potential are eligible to participate after a negative highly sensitive pregnancy test if they are taking a highly effective method of contraception during treatment and until the end of relevant systemic exposure. As the oral contraceptive is an exclusion criterion, the following methods are permitted:
 - sexual abstinence
 - intrauterine device (also called IUD)
 - intrauterine hormone-releasing system (also known as IUS)
 - bilateral tubal occlusion
 - vasectomised partner

*Definition of fertile females (women of childbearing potential) and of fertile men:

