6.9 Unscheduled visit (when needed)

This type of visit can be performed at any time during the study, when the patient/study physician finds it necessary. For example, an unscheduled visit can be performed if the patient experiences discomfort at home due to ankle swelling that needs further investigation. In every unscheduled visit, the patient will undergo the following procedures:

- Physical examination
- Concomitant medications
- Document AEs
- Vital signs: (i) Resting supine BP, (ii) pulse measurement, (iii) temperature, (iv) pulse oximetry (incl. respiratory rate), and (v) weight

- ECG*
- Echocardiogram*
- Blood samples for haematology and clinical chemistry*
- Urinary pregnancy test (if indicated)

*if clinically required.

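### Scheduled pregnancy testing stops at Week 8, when dosing ends, and the existing Week 12 off-drug visit has no test, so the schedule cannot reliably show conceptions late in dosing

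*Protocol*

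**What the plan says.** Section 4.1 sets the timeline: "The total period of treatment for each patient is 8 weeks, followed by 4 weeks follow up off XBD173". The study summary agrees: "They will be followed for a further 4 weeks off study treatment".

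Section 4.3.1, inclusion criterion 9, requires of women of childbearing potential a negative pregnancy test and a "highly effective method of contraception during treatment and until the end of relevant systemic exposure". The end of that exposure is not given in days.

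Scheduled tests are as follows:

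- a serum test at screening (6.1), "for women of childbearing potential";
- urine tests, where indicated, at baseline (6.2), Week 2 (6.4), Week 4 (6.6) and Week 8 (6.7), the last with a window of ± 3 days.

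For Week 12, section 6.8 says that "a home assessment will be made at the end of Week 12 in order to undergo the following procedures". It then lists physical examination, concomitant medications, adverse events, vital signs, ECG and research blood, but no pregnancy test. In Appendix 1 the row "Urinary pregnancy test" is marked at Weeks 0, 2, 4 and 8 and for unscheduled visits, and is blank at Week 12.

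Outside the fixed visits, section 6.9 allows an unscheduled visit at any time "when the patient/study physician finds it necessary", with a urine test if indicated. Under section 4.3.4, pregnancy is a ground for discontinuation, and early terminators receive a telephone assessment at 4 weeks.

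**The concern.** The contraception rule treats pregnancy as a matter of concern until some point after the last dose. Scheduled testing stops at the last dose. A urine test does not turn positive on the day of conception, so a test at the end of dosing says least about the final stretch of dosing. A visit at a suitable time, four weeks off drug, already exists and carries no test.

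What is at stake is recognising a pregnancy exposed to XBD173, so that the woman can be advised and followed. No objective, endpoint or dosing decision depends on it.

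**Working it through.** The plan gives no figure on this point to reproduce. The check compares the visit lists with the schedule and then counts days.

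**Text against schedule.** Sections 6.2, 6.4, 6.6 and 6.7 each name a urine test; section 6.8 does not. The urine-test row of Appendix 1 shows the same pattern. Because the two sources agree, the blank Week 12 cell is neither a table-reading artefact nor a slip between text and table.

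**Inputs from the protocol**

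- Last dose: end of Week 8, nominal day 8 × 7 = 56 (4.1).
- Week 8 visit: 56 ± 3, so days 53 to 59 (6.7).
- Week 12 visit: 12 × 7 = 84, ± 3, so days 81 to 87 (6.8).

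**Assumption, not in the documents.** The lag from conception to a positive urine test is L = 10 to 21 days.

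**Uncovered part of dosing.** A test on day T can show conceptions up to about day T − L. If dosing ends on day T, the last L dosing days are uncovered, a share of L / T.

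| Week 8 visit and last dose | L = 10 | L = 21 |
|---|---|---|
| Day 56 (nominal) | 10/56 = 17.9% | 21/56 = 37.5% |
| Day 53 | 10/53 = 18.9% | 21/53 = 39.6% |
| Day 59 | 10/59 = 16.9% | 21/59 = 35.6% |

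With a shorter lag of 7 days the nominal share is 7/56 = 12.5%. The direction holds for any lag above zero; only the size depends on L. Any exposure after the last dose adds to the uncovered time but cannot be quantified, because its length is not given.

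**Would a Week 12 test close the gap?** The interval between the Week 8 and Week 12 visits is:

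- nominal: 84 − 56 = 28 days;
- shortest: 81 − 59 = 22 days;
- longest: 87 − 53 = 34 days.

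Even the shortest interval exceeds the longest assumed lag (22 > 21). A conception up to a last dose at the Week 8 visit would therefore be detectable. At the nominal days the test would also reach conceptions up to 28 − 21 = 7 to 28 − 10 = 18 days after the last dose. This holds only for women who attend Week 12.

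**The case against.** The strongest reply is that nothing here is wrong on the protocol's own terms. Text and schedule agree. The duty to use contraception beyond the last dose is not a promise to test beyond it. The existing tests serve the decisions for which pregnancy matters, namely exclusion and discontinuation; after Week 8 there is no drug left to stop. Highly effective contraception is required, there are up to 6 participants, and a woman or her physician can prompt an unscheduled test at any time.

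Much of this stands. A reader might infer that the protocol contradicts itself; it does not. A reader might also infer that a late conception could not be found at all. That too goes too far, because section 6.9 allows a test if indicated, and adverse events are recorded at Week 12. The limitation is one of scheduled testing only. Neither route replaces a scheduled test, however, since an unrecognised early pregnancy may trigger neither. Small numbers and effective contraception applied equally when tests were placed at Weeks 2, 4 and 8.

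A further temptation is to widen the gap by moving the Week 8 visit within its window while holding the last dose at day 56. That gives 10 − 3 = 7 to 21 + 3 = 24 days. The documents do not support it well. Section 6.7 has drug collected and reconciled at the Week 8 visit, which suggests that dosing ends there, although collection is also listed at Week 4 and, in Appendix 1, at Week 12. If dosing ends at the visit, the gap is 10 to 21 days whatever the visit day.

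It is also fair to say that section 8 sets out no pregnancy-specific reporting or follow-up, so a positive result would lead to clinical care rather than to a defined protocol step.

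**Conclusion.** The point holds as a cheap improvement. Scheduled testing ends with dosing, and so cannot reliably show conceptions in about the last 10 to 21 of 56 dosing days, or during any exposure after the last dose. The 10 to 21 days rest wholly on the assumed detection lag.

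The 18 to 38% is a share of dosing time. It should not be read as a chance that a pregnancy is missed: expected events are near zero, because only some of the up to 6 participants will be of childbearing potential, and those must use highly effective contraception. Trial conclusions are unaffected.

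**What to change.** Add a urinary pregnancy test, if indicated, to the procedures in section 6.8, and mark the Week 12 cell of the urine-test row in Appendix 1 with footnote a (women of childbearing potential only). The home option is no obstacle: the baseline column is also clinic or home and already carries the test.

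The cost is one urine test per woman concerned, at a visit that already takes place. There are two limits. The result comes too late to alter dosing and serves only to identify an exposed pregnancy for care and follow-up. Women who stop early and receive only the 4-week telephone call (4.3.4) are not covered by this change.
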